HIGH FAT VS HIGH PROTEIN AND APPETITE HORMONES

NCT # 04518930

Document Date: 03/06/2024

Study protocol

Study design and participants

The study design utilized a parallel-arm intervention, employing a non-blind randomized clinical trial format with two distinct treatment groups. This study enrolled fifty-two healthy Jordanian women from a private nutrition clinic in Amman through randomization.

This study was conducted in accordance with the ethical guidelines outlined in the Declaration of Helsinki. The research procedures involving study participants received approval by the Institutional Research Board committee at the University of Jordan (No. 19/2021/180). Furthermore, the study was registered on ClinicalTrials.gov (No. NCT 04518930). Written informed consent was obtained from all individuals who participated in the study.

Inclusion and exclusion criteria

The study's inclusion criteria encompassed women aged between 30 and 40 years, with a body mass index (BMI) ranging from 25 to 35 kg/m². The included age group comprises predominantly overweight and obese individuals attending the nutrition clinic, demonstrating high adherence to the study protocol. These individuals engaged in light exercise 1-3 times per week (activity factor 1.375) and adhered to a routine of consuming three regular meals, along with two daily snacks. They maintained a water intake of eight cups and ensured a sleep duration of 8 hours. Additionally, participants were required to have no known allergies, particularly to nuts, especially peanuts and yogurt.

Conversely, women were ineligible for the study if they met any of the following conditions: age below 30 years or above 40 years, BMI below 25 kg/m² or above 35 kg/m², engaged in little or no exercise or engaged in moderate to heavy exercise, were pregnant or lactating mothers, had allergies to nuts, peanuts, yogurt, milk, or milk products, were

using medications, hormonal therapy, supplements, oral contraceptives, or herbal/botanical products claimed to suppress appetite. Furthermore, exclusion criteria encompassed women with hormonal disturbances, including those in a menopausal state, and those within their menstrual cycle days or within one week prior, commonly experiencing hyperphagia due to elevated progesterone levels. Additionally, individuals with chronic diseases and metabolic disorders such as cardiovascular diseases, diabetes, hypertension, kidney diseases, thyroid disorders, gastrointestinal diseases, polycystic ovary syndrome, or androgen disorders were excluded, following a weight-reducing diet, experiencing sleep disorders, or sleeping less than 8 hours per day, and consuming less than 8 cups of water per day were also excluded from the study.

Sample size determination

The required sample size for the study was determined using the formula:

$n = 2 * (Z\alpha + Z\beta)^2 * SD^2 \div \delta^2$, where n represents the required number of participants in both the treatment and placebo groups. $Z\alpha$ and $Z\beta$ are the values from the standard normal distribution corresponding to specific confidence levels of 95% and a two-sided α of 0.05 ($Z\alpha = 1.96$) and a power of 80% ($Z\beta = 0.84$). SD refers to the standard deviation (pooled), while δ represents the estimated difference between the treatment and placebo groups.

Based on the above equation, the sample size calculation indicated that approximately 20 subjects were needed for each arm of the trial to detect a change of 1.76 μ U/mL in insulin levels between the treatment and placebo groups, with 80% power and 5% significance. The standard deviation

(SD) was assumed to be 2.1. Therefore, $n = 2 * (1.96 + 0.84)^2 * (2.1)^2 \div (1.76)^2 \approx 22$ participants per group.

To account for potential participant dropouts and to enhance the statistical power of the analysis, the number of participants was increased to 26 women per group.

Overview of the study design and procedures

The study employed a two-arm parallel design, consisting of 52 participants who were randomized into two groups. The Greek yogurt group ($n = 26$) received one serving (380 g, 200 kcal) of zero-fat Greek yogurt, and the peanut group ($n = 26$) received one serving (35 g, 200 kcal) of unsalted peanuts. Due to one participant from each group dropping out and not attending the second visit, only 25 subjects were included in the study analysis in each group.

All participants attended two visits to the clinic. During the initial visit, participants were instructed to arrive fasting for 10-12 hours, during which anthropometry and body composition analysis were conducted. They also received education and instructions to follow a three-day low-calorie diet totaling 1200 kcal, comprising breakfast, snack 1, lunch, snack 2, and dinner, prior to the interventions. On the second visit (post-diet visit), participants received and consumed their snacks, completed the visual analog scale (VAS) questionnaire and blood samples were withdrawn.

Treatment/intervention and randomization

Intervention

Two distinct interventional snacks were provided to the participants: plain Greek yogurt and peanuts. In the Plain Greek yogurt group ($n=25$), each participant consumed 380g of plain Greek

yogurt, equating to approximately 200 calories. In the peanut group, (n=25) each participant consumed 35g of roasted, unsalted peanuts, providing approximately 200 calories.

The plain Greek yogurt (non-flavored /30g protein/13.5g carbohydrate/0g fat) was procured from the supermarket and stored in the refrigerator until serving. The peanuts (roasted, unsalted, with skin/ 8.4g protein/7.6g carbohydrate/17.5g fat) were purchased one day prior to the serving date to preserve their attributes. They were meticulously prepared in a safe and sterile manner, portioned into small transparent pouches, each containing 35g. These packed peanuts were then stored in a dry, room-temperature environment until the serving date. Table 1 shows the macro and micronutrients composition of the two interventional snacks.

The intervention was provided to each participant upon arrival at the clinic based on pre randomization and they were asked to consume it at 1:00 pm.

Randomization

The participants were assigned to two groups sequentially, following a predetermined randomization list. "Peanut" and "Greek yogurt" were each written clearly in Arabic on 26 folded papers. The list was created by randomly selecting folded papers from a basket, each containing either the label "peanut," or "plain Greek yogurt". The groups were then identified as the peanut group and the Greek yogurt Group based on the random selection of each participant .

All participants adhered to a 1200 kcal diet plan, including breakfast, snack 1, lunch, snack 2, and dinner. This diet plan remained consistent for all participants over three consecutive days, except during the second visit, where specific snacks were provided based on the randomization list.

Data collection and assessment

Pre-diet visit

During the initial visit, participants were provided with a three-day low-calorie diet menu totaling 1200 kcal. This menu included breakfast, snack 1, lunch, snack 2, and dinner, along with a follow-up sheet. They were instructed to adhere to the foods listed in the diet menu and to refrain from consuming peanuts or any peanut-based products, as well as Greek yogurt, during snack 1 and snack 2. Additionally, they were briefed on the necessity of daily follow-up via phone to monitor their compliance with the given instructions. Body composition analysis was performed using bioelectrical impedance analysis (Inbody 770). To categorize participants into groups, they were randomly allocated based on a pre-determined randomization list.

Anthropometric and body composition analysis

Before the body composition analysis test, each participant visited the clinic after overnight fasting for a period of 10-12 hours. The analysis was conducted using bioelectrical impedance technology, which automatically recorded several parameters, including weight, height, BMI, skeletal muscle mass, soft lean mass, fat mass, and abdominal circumferences. To ensure precise readings, participants were advised to wear lightweight clothing and remove any metal items, such as accessories, belts, money, and socks before the test.

Post-diet visit

On the second visit, scheduled after three days of adhering to the 1200 Kcal diet, all participants arrived at the clinic at 1:00 pm. Prior to their arrival, they had breakfast at home at 9:00 am. Upon arrival, a trained healthcare professional collected baseline blood samples from each participant.

At 1:00 pm, participants in the plain Greek yogurt and peanut groups consumed their assigned snacks. Following snack consumption, a validated VAS questionnaire was distributed to assess sensations and appetite levels at 0 minutes (1:00 pm), 30 minutes (1:30 pm), and 60 minutes (2:00

pm). Additionally, one hour after their arrival, at 2:00 pm, a second blood sample was collected from all participants. Throughout this period, participants were situated in a stress-free environment designed for relaxation and comfort, with soft music played to enhance their experience. No adverse events were reported by any of the participants following snack consumption.

Appetite perceptions

Appetite sensation was evaluated using a validated VAS questionnaire, designed to measure subjective ratings of hunger, fullness, satiety, prospective food consumption, and desire to eat. The VAS questionnaire included questions assessing “how strong is your feeling of” hunger, fullness, and desire to eat or “how much food can you eat right now” with anchors of “not (much) at all” to “extremely/an extreme amount”.

Participants were instructed to indicate their sensations on the scale at various time points during the study: upon arrival, 30 minutes, and 60 minutes after consuming the snack. This allowed us to discern the impact of consuming Greek yogurt and peanuts on appetite perceptions over time. The decision to assess at 30 and 60 minutes was based on the rapid increase in gut hormones following food intake, with their secretion peaking around 1-2 hours later. The VAS questionnaire was self-administered, ensuring a convenient and straightforward assessment for the participants.

Biochemical analysis

The collected blood samples (baseline and after 60 minutes of intervention) were labeled with a unique code to ensure proper identification before being transported to the medical laboratory.

The blood samples were drawn into plain tubes containing separation gel and left undisturbed until coagulation occurred. After coagulation, serum was separated from the blood cells through centrifugation at 882 $\times g$ for 20 minutes. The resulting serum was then carefully transferred into Eppendorf tubes and stored at -20 °C to preserve the integrity of the peptides for subsequent analysis. These storage procedures adhered to the recommendations outlined in studies conducted by Hallworth and Lobely.

All biochemical blood assays were conducted in duplicate, and the average of these duplicate measurements was utilized in the statistical analysis.

CKK, PYY, GLP-1 and insulin analysis

The blood samples were sent to the laboratories of Aurum Biotechnology Company, where the researcher conducted the analysis following the instructions provided in the respective manuals. The analysis utilized the following ELISA kits: Human PYY ELISA kit (Lot No: 9680012101) (catalog no. RK02174; ABclonal, USA), Human GLP-1 ELISA kit (Lot No: 9680012107) (catalog no. RK09098; ABclonal, USA), Human CCK ELISA kit (Lot No: 1210528141) (catalog no. MBS770851; MyBioSourceA) and Human Insulin ELISA kit (lot No: 9680004240821) (Catalog. no. RK 00302; ABclonal, USA).

Ghrelin analysis

The analysis of GHRL (ghrelin) was carried out using the Human GHRL ELISA kit (Lot No: 38401422) (catalogue no. MBS2602099; MYBioSource, USA). This kit utilizes the Competitive-ELISA method. The well plates used for the analysis were pre-coated with GHRL. In the reaction, the GHRL present in the sample or standard competed with a fixed amount of GHRL on the solid phase supporter for binding sites on the Biotinylated Detection Antibody specific to

GHRL.

Statistical analysis

The statistical analysis was conducted using SPSS version 25.0 (IBM SPSS Statistics for Windows, IBM Corporation). Before analysis, a nonparametric Kolmogorov-Smirnov test was employed to assess the normal distribution of all continuous variables. Descriptive statistics were used to assess the frequencies of categorical variables, while means \pm standard deviations (SD) were calculated for continuous variables.

To determine differences between the means of normally distributed continuous variables in both the plain Greek yogurt and peanut groups, a Student t-test for independent samples was employed. Additionally, a paired sample t-test was used to assess variations in means of normally distributed variables before and after snack consumption in both groups. In instances where variables displayed significantly skewed distributions, medians were compared using the Mann-Whitney U test for independent samples, while paired samples were compared using the Wilcoxon Signed Rank test. A two-way repeated measures ANOVA was performed to test the main and interaction effects of Greek yogurt, peanuts, and time on appetite and insulin hormones. Additionally, the repeated measures procedure of the General Linear Model (GLM) was utilized to analyze the impact of plain Greek yogurt and peanuts on appetite perceptions over time. Correlations between gut hormones, insulin, and anthropometric measurements were assessed using the Pearson two-tailed bivariate test for continuous variables. All p-values are two-tailed, and a significance level of $p \leq 0.05$ was considered.

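### Visit-1 BMI is used neither to stratify allocation nor to adjust any between-arm analysis, although eligibility spans BMI 25 to 35; the cost is modest precision, not bias

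*Combined protocol and SAP*

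**What the plan says.** All places are in the combined protocol and SAP.

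- **Inclusion and exclusion criteria:** women are eligible "with a body mass index (BMI) ranging from 25 to 35 kg/m²", so overweight and obese women enter together.
- **Randomization:** 26 papers are labelled for each snack. "The list was created by randomly selecting folded papers from a basket" describes the draw. Arm sizes are fixed at 26, and no stratification factor is named.
- **Anthropometric and body composition analysis:** BMI and fat mass are recorded at the first visit, before the snack.
- **Statistical analysis:** the between-arm methods are the independent t-test, the Mann-Whitney test for skewed variables, a two-way repeated-measures ANOVA (snack, time and interaction) for the hormones, and a repeated-measures GLM for the appetite ratings. No covariate is named. Body size is given an analytic role in one sentence only: "Correlations between gut hormones, insulin, and anthropometric measurements were assessed using the Pearson two-tailed bivariate test for continuous variables".
- **Overview of the study design and procedures:** after one dropout per arm, "only 25 subjects were included in the study analysis in each group".

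**The concern.** BMI is known before the snack, varies over a ten-unit range by design, and is of enough interest to be correlated with the outcomes. Yet it plays no part in allocation or in estimating the snack effect. With 25 women per arm, chance can leave the arms visibly different in body size. If BMI is related to an outcome, two things follow. Explainable variance stays in the error term. And a reader who sees unequal BMI cannot tell how far the result depends on it. Independent t-tests on 60-minute values are the most exposed, because they do not use each woman's own starting value.

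**Working it through.** **Inputs from the documents.** Alpha is stated as "a two-sided α of 0.05" with 80% power; the insulin difference is 1.76 µU/mL and the SD 2.1 (Sample size determination). There are 26 randomised and 25 analysed per arm.

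**Assumptions, because the documents give no figure.** Obese means BMI of 30 or more. K, the number of obese women among the 52, is 20 to 32 (about 40 to 60%). The correlation r between BMI and the outcome is 0.1 to 0.5, with most weight on 0.2 to 0.3.

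**1. The plan's own figure.** n = 2(1.96 + 0.84)² × 2.1² ÷ 1.76² = 22.3 per arm, which agrees with the stated 22 (23 if rounded up). The same paragraph also says approximately 20; that is a separate matter.

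**2. Power as analysed, unadjusted.** SE = 2.1 × √(2/25) = 0.594. 1.76 ÷ 0.594 = 2.963. Power = Φ(2.963 − 1.96) = 84.2% (82.7% by the t distribution).

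**3. Chance imbalance in the obese share at randomisation.** The number of obese women in one arm, X, is hypergeometric (52 women, K obese, 26 drawn), and the arms differ by |2X − K| women. If K is even the difference is even; if K is odd it is odd. So the attainable step nearest 20 points is 6/26 = 23.1 points for even K and 5/26 = 19.2 points for odd K.

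| K | Step | Chance of at least this difference |
|---|---|---|
| 20 or 32 | 23.1 points | 15.3% |
| 22 or 30 | 23.1 points | 16.0% |
| 26 | 23.1 points | 16.5% |
| 21 or 31 | 19.2 points | 25.8% |
| 25 or 27 | 19.2 points | 26.7% |

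A strict 20-point cut should not be applied across all K. For odd K it would skip 19.2 and count only 7/26 = 26.9 points or more (8.9% at K = 21), an apparent drop caused only by parity.

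**4. Chance imbalance in mean BMI, 25 per arm.** The standardised mean difference has SD √(2/25) = 0.283. P(|difference| ≥ 0.25) = 38%; P(|difference| ≥ 0.5) = 7.7%.

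**5. What such an imbalance does to one realised comparison.** Shift in unadjusted insulin = r × standardised difference × 2.1. At 0.5 this is:
- r = 0.1: 0.11 µU/mL, 6% of 1.76
- r = 0.3: 0.32 µU/mL, 18%
- r = 0.5: 0.53 µU/mL, 30%

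Over repeated allocations the shift averages zero.

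**6. Power with BMI in the model.** Residual SD = 2.1 × √(1 − r²); power as in step 2.

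| r | Residual SD | Power |
|---|---|---|
| 0.1 | 2.089 | 84.6% |
| 0.2 | 2.058 | 85.6% |
| 0.3 | 2.003 | 87.4% |
| 0.5 | 1.819 | 92.8% |

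**7. With the pre-snack value already in the model.** BMI's further contribution is its squared partial correlation. As an illustration, suppose pre- and post-snack values correlate 0.5 and BMI correlates 0.3 with each. The partial correlation is (0.3 − 0.5 × 0.3) ÷ √(0.75 × 0.91) = 0.18. BMI then removes about 3% of the residual variance, against 0.3² = 9% on its own.

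**The case against.** The strongest reply is that this is an optional refinement. Randomisation makes the unadjusted comparison unbiased, and the two-sided alpha already allows for chance imbalance. Power with 25 per arm exceeds the planned 80% without adjustment. Simple allocation with fixed arm sizes is acceptable in a small single-clinic trial. The snack-by-time interaction compares each woman with her own pre-snack value, so stable BMI-related differences in level cancel. The appetite model is also repeated-measures, with a rating at 0 minutes. All of this stands, and it limits the point to precision and robustness. What remains uncovered is any effect of BMI on the response to the snack, and t-tests on absolute 60-minute values.

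Three stronger readings are tempting and unsupported:

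- **That the plan expects BMI to track the hormones.** It only tests correlations with anthropometric measurements. It states no direction, strength or expectation, and that sentence does not name BMI. The correlations do not extend to the appetite ratings.
- **That BMI imbalance biases or confounds the trial.** A chance difference can move one realised estimate (step 5), but it is not a systematic error.
- **That BMI is never compared between arms.** The general t-test sentence could cover a descriptive comparison. What is absent is BMI as a stratifier or covariate.

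**Conclusion.** The point holds as a minor, inexpensive improvement. BMI is available and unused in every between-arm analysis named. At r of 0.2 to 0.3 the gain is 1.4 to 3.2 percentage points of power (84.2% to 85.6% or 87.4%), and less once the pre-snack value is included. A gain near 9 points needs r = 0.5, for which the documents offer no support. An imbalance of 19 to 23 points or more in the obese share has a chance of roughly 15 to 27%, if about 40 to 60% of the women are obese. These sizes rest on the assumed obese share and correlation, and on reading 2.1 as the SD of the insulin quantity compared between arms. Nothing here invalidates the planned comparisons.

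**What to change.** Report visit-1 BMI by arm. In the between-arm models for the hormones and insulin, add continuous visit-1 BMI as one covariate alongside the pre-snack value: for example, an ANCOVA of the 60-minute value on arm, pre-snack value and BMI. The same term can be added to the appetite-rating model beside the 0-minute rating, presented as an extension that the plan's own correlations do not cover. Give the adjusted result next to the unadjusted one, so that readers can see whether the conclusion depends on how BMI fell between the arms.

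The document reports completed allocation and dropouts, so stratified lists can no longer be drawn. A covariate added now cannot be called pre-specified; label the analysis post hoc unless a record shows that it was specified before the data were seen.

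The cost is one model term and one degree of freedom. No new data are needed.

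### In a non-blind trial that assigns women in order from a pre-drawn list, no step is described that hides the next arm until eligibility is settled

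*Combined protocol and SAP*

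**What the plan says.** Study design and participants describes a trial "employing a non-blind randomized clinical trial format with two distinct treatment groups".

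The Randomization section says: "The participants were assigned to two groups sequentially, following a predetermined randomization list". The two snack labels "were each written clearly in Arabic on 26 folded papers", and "The list was created by randomly selecting folded papers from a basket". The papers thus generate a sequence with 26 entries per arm, in effect one block of 52. The Pre-diet visit section repeats the point: "To categorize participants into groups, they were randomly allocated based on a pre-determined randomization list".

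Inclusion and exclusion criteria sets several narrow entry rules. Women "sleeping less than 8 hours per day, and consuming less than 8 cups of water per day were also excluded from the study". Only light exercise, one to three times a week, qualifies. Women who are menstruating, or within the week before, are ineligible. No method of ascertaining sleep, water intake, exercise or cycle day is given.

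The document does not say who drew, held or could see the list, or whether eligibility was recorded before the next entry was read. It mentions no envelopes, independent holder or screening log.

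For the hormones and insulin, blood is taken before the snack and again at 60 minutes. Statistical analysis plans independent t-tests or Mann-Whitney tests between arms, paired tests within arms, and a two-way repeated measures ANOVA with main and interaction effects. Appetite ratings get a repeated measures general linear model.

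**The concern.** Randomisation protects the yogurt-versus-peanut comparison only if the decision to enter a woman is independent of the arm she would receive. Drawing papers to build a list makes the order random, but it does not keep that order from the person deciding entry.

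The entry rules leave room for judgement. Whether someone sleeps 8 hours or drinks 8 cups is a sharp cut on a quantity with no stated measurement. The cycle rule also gives an ordinary reason to rebook a woman, which moves her to another place in a list used in order. A person who knows the next entry could accept, decline or postpone a borderline woman accordingly. Placing allocation at one visit rather than another does not remove this, because the order exists before any woman is screened.

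If that happened, the arms could differ for reasons other than the snack, and some of the planned tests would count the difference as a snack effect.

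**Working it through.** **1. The plan's own figure.** Sample size determination gives n = 2 × (1.96 + 0.84)² × 2.1² ÷ 1.76² = 2 × 7.84 × 4.41 ÷ 3.0976 = 22.32 per group. The stated figure of about 22 reproduces (23 if rounded up). Concealment does not alter it; only the SD of 2.1 is used below.

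**2. Foreseeability of the next assignment.** Inputs: 26 papers per label, no blinding, assignment in list order.
- List visible to the enroller: 52 of 52 known. This follows directly from the assumption of visibility.
- List hidden, past assignments known, enroller always guesses the arm with more papers left: expected correct guesses = 26 + (4²⁶ ÷ C(52,26) − 1) ÷ 2 = 26 + (9.081 − 1) ÷ 2 = 30.04, and 30.04 ÷ 52 = 57.8%. Pure chance gives 26 of 52, or 50%.
- In that hidden case, the expected number of assignments certain at the end = 2 × 26 ÷ 27 = 1.93.

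A simulation of 10,000 lists gave 30.06 and 1.91. The second and third figures describe a concealed list. Envelopes would bring an open list down to this level but not below it.

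**3. Which planned analyses would carry a bias.** Let τ be the true difference in snack effect, b a constant shift in one arm present before and after the snack, and r a difference in how the selected women respond.
- Between arms, post-snack level: τ + b + r.
- ANOVA group main effect (average over the two times): [b + (b + τ + r)] ÷ 2 = b + (τ + r) ÷ 2.
- Group-by-time interaction, or difference in changes: τ + r. The shift b cancels.
- Paired test within an arm: b cancels from the change; a difference in response does not.
- Post-snack level adjusted for the pre-snack value with slope β: τ + r + (1 − β)b. For β between 0 and 1 this reduces b; it removes it only if β = 1.

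The plan does not say whether the between-arm t-test or Mann-Whitney test uses levels or changes, and states no baseline adjustment. The b term applies if levels are used.

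For appetite ratings the baseline is unclear. The Post-diet visit section has the questionnaire handed out after the snack, with time 0 at 1:00 pm. The Appetite perceptions section has the first rating on arrival. If the first rating follows eating, there is no clean pre-snack value to cancel against.

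**4. Sensitivity only.** Suppose τ = 0 and selection leaves an assumed difference of d SD between arms in the quantity tested. Take a two-sided 5% t-test with 25 per arm, 48 degrees of freedom and noncentrality d × √(25 ÷ 2).

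| Assumed d (SD) | In µU/mL (d × 2.1) | Noncentrality | Rejection rate |
|---|---|---|---|
| 0 | 0 | 0 | 5.0% |
| 0.1 | 0.21 | 0.354 | 6.4% |
| 0.2 | 0.42 | 0.707 | 10.7% |
| 0.3 | 0.63 | 1.061 | 18.0% |

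Nothing in the document supplies d.

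**The case against.** **Silence is not proof of an open list.** A list made in advance is normal, and an independent person may have held it. The Randomization section also says groups were identified "based on the random selection of each participant", which could hint at a draw for each woman. This stands in part. A reader might infer that the list was visible, or that women were in fact selected; the document supports neither. It supports only that no safeguard is described. The per-woman reading sits badly with a list made beforehand, and it too comes without a safeguard.

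**The criteria may be firmer than they look.** Self-report is an inference from the absence of a stated method. BMI is recorded by the body composition device, exercise frequency is a range rather than a single cut, and the meal pattern is a routine. This stands, so the point is limited to criteria with no stated measurement.

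**The baseline sample protects the hormone analysis.** This stands for a constant shift in the paired tests and the interaction. It would therefore be wrong to infer that every planned test would mistake a baseline difference for a snack effect. It does not cover unadjusted between-arm tests on levels, the group main effect, selection on response, or appetite ratings.

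**The bias can be put as a percentage of the planned difference.** A reader might suppose that 10–30% of one arm are borderline women differing by 0.5–1 SD. That gives 0.10 × 0.5 × 2.1 = 0.105 to 0.30 × 1 × 2.1 = 0.63 µU/mL, or 6–36% of 1.76. The document does not support this as an estimate. The inputs are assumed, the calculation puts no borderline women in the other arm, and nothing links sleep or water intake to insulin. The plan calls 1.76 a change without saying whether the SD of 2.1 refers to levels or changes.

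**The trial is finished.** The Overview section reports 25 analysed per group, so envelopes cannot help this run. That stands and shapes the fix.

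**Conclusion.** The point holds as a weakness in the described procedure that should be corrected, with medium confidence. Non-blind conduct, a list made beforehand and used in order, and no described barrier between list and eligibility decision together make selective entry possible.

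The size that can be stated is predictability: 100% of assignments if the list was visible, against 57.8% if it was hidden and past assignments were known. The size of any bias is unknown. The rejection rates of 6.4% to 18.0% rest on assumed differences of 0.1 to 0.3 SD and show sensitivity only.

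The exposure is uneven. It is greatest for unadjusted between-arm comparisons of levels, the ANOVA group main effect and the appetite ratings. For the hormone interaction it is confined to selection on response, provided any baseline shift is constant over the hour. The sample size is unaffected.

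**What to change.** **In the allocation procedure.** Keep the folded-paper draw, but have a colleague not involved in recruitment seal each paper in a sequentially numbered opaque envelope. Record and sign the full eligibility checklist first, including the sleep, water, exercise and cycle-day answers. Then write the woman's code on the next envelope and open it. Keep a log of women screened and rejected, with reasons. The cost is 52 envelopes, one signature per woman and a log, with no extra participants or procedures.

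**For the trial as run.** State who generated and held the list, whether eligibility was recorded before the next entry was seen, and how many women were screened and rejected, with reasons. Show baseline values by arm. If allocation was not concealed, say so and limit the causal claim. Base the hormone comparison on the group-by-time interaction or a baseline-adjusted between-arm analysis rather than unadjusted post-snack tests. State whether the first appetite rating preceded the snack. This needs existing records and a reanalysis of existing data; if no screening records were kept, that should be stated.

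### Allocation at visit 1, before a run-in common to both arms, leaves the compliance calls and the visit-2 baseline open to knowledge of the arm in a non-blind trial

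*Combined protocol and SAP*

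**What the plan says.** - **Blinding.** Study design and participants describes the trial as "employing a non-blind randomized clinical trial format with two distinct treatment groups".
- **Time of allocation.** The Pre-diet visit section, after the menu, the instructions and the body composition measurement, states: "To categorize participants into groups, they were randomly allocated based on a pre-determined randomization list". The Intervention section agrees: "The intervention was provided to each participant upon arrival at the clinic based on pre randomization".
- **Method.** Randomization: "The participants were assigned to two groups sequentially, following a predetermined randomization list". The list was drawn from 26 folded papers per arm. No concealment step is described.
- **When the arms diverge.** Randomization: "This diet plan remained consistent for all participants over three consecutive days, except during the second visit, where specific snacks were provided". The Pre-diet visit section tells all women to avoid both peanuts and Greek yogurt at the two daily snacks.
- **Contact during the run-in.** Pre-diet visit: "they were briefed on the necessity of daily follow-up via phone to monitor their compliance with the given instructions".
- **Loss.** The Overview counts 52 randomised and explains the 25 analysed per arm: "Due to one participant from each group dropping out and not attending the second visit".

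**The concern.** Nothing in the run-in depends on the arm, so allocating before it gains nothing scientifically. It does open a period of about three days in which a caller, a sampler or a participant could know the arm before any arm-specific treatment is given. Such knowledge could alter how compliance is coached, who attends visit 2, and how a woman rates her hunger before the snack.

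The planned analyses use those values. The Statistical analysis section lists before/after paired tests, a two-way repeated measures ANOVA on the hormones and a repeated measures GLM on appetite. A baseline taken after allocation, with no protection against knowledge of the arm, is a weaker reference for all of them.

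Allocating early also means that a woman who never returns for visit 2 counts as randomised but is not treated or analysed.

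**Working it through.** **1. Did allocation precede visit 2?** Three statements agree. The allocation sentence stands under the Pre-diet visit. The snack at visit 2 followed an earlier randomisation (Intervention). The two women who missed visit 2 are each counted in an arm (Overview), which requires that they had already been allocated.

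**2. What falls between allocation and snack?**

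| Item | Where described | Exposure to knowledge of the arm |
|---|---|---|
| Body composition, visit 1 | Anthropometric and body composition analysis | Little: recorded automatically, described before the allocation sentence |
| Daily compliance calls, diet adherence | Pre-diet visit | Yes, if the caller or the woman knew the arm |
| Baseline blood, visit 2 | Post-diet visit | Mainly indirect, through run-in behaviour; the hormones are assayed |
| 0-minute VAS, visit 2 | Post-diet visit; Appetite perceptions | Most: subjective and self-administered |

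**3. Is the baseline VAS before the snack?** The Post-diet visit section has the VAS handed out after the snack was eaten, with a 0-minute rating at 1:00 pm. Appetite perceptions puts the first rating at arrival. Arrival and snack are both set at 1:00 pm. The text does not settle whether this rating precedes the snack.

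**4. The plan's own sample size.** Inputs from Sample size determination: difference 1.76, SD 2.1, Z values 1.96 and 0.84.

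n = 2 × (1.96 + 0.84)² × 2.1² ÷ 1.76² = 2 × 7.84 × 4.41 ÷ 3.0976 = 22.3 per group. The stated 22 is reproduced.

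**5. Size of the loss.** 1/26 per arm; 2/52 = 3.8% overall (exact 95% CI 0.5% to 13.2%).

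**6. Power after the loss.** The standardised difference is 1.76 ÷ (2.1 × √(2/n)).
- n = 25: 1.76 ÷ 0.594 = 2.963. Power = Φ(2.963 − 1.96) = 84.2% (82.7% by the noncentral t).
- n = 26: 1.76 ÷ 0.582 = 3.022. Power = Φ(3.022 − 1.96) = 85.6% (84.2% by the noncentral t).

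The loss costs about 1.5 points, and power stays above the planned 80%.

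**7. Could the two missing women matter to the estimate?** The documents give no values for them, so this is an assumption. If each differed from the mean of the other 25 in her arm by k SD, in opposite directions, the insulin difference would move by 2 × k × 2.1 ÷ 26.
- k = 0.5: 0.08 μU/mL, 5% of 1.76
- k = 1: 0.16 μU/mL, 9%
- k = 2: 0.32 μU/mL, 18%

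**The case against.** The strongest reply is that no harm is shown. The document nowhere says that women or callers knew the arm during the run-in. Everyone had the same menu and the same ban on both foods, and the snack was handed over at the clinic, which fits women learning their arm only at visit 2. The non-blind label does not show that the person who made the calls held the list. All of this stands, and it limits the point to a risk without a stated safeguard.

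Three stronger readings are tempting, and the documents do not support them.

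- **That the baseline is biased.** This requires knowledge of the arm before the snack. The time of disclosure is simply not stated.
- **That the false-positive rate is inflated by a known amount.** One can assume a pre-snack shift of 0.2 SD and obtain a rejection rate of about 11% at 25 per arm (0.2 × √12.5 = 0.707, giving 0.105 + 0.004 = 0.109). The shift is invented, however, and the result applies only to unadjusted comparisons of post-snack means. A constant additive shift present before and after the snack cancels from the group-by-time interaction in the planned repeated measures analyses. The figure should not be used as evidence.
- **That the loss breaks the randomised comparison.** It was one woman per arm, before the arms received anything different, and neither has outcome data. Later allocation at the same enrolment would still yield 50 women. The Overview already discloses the dropouts and the reason.

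It is also fair to say that yogurt and peanuts cannot be disguised, so the 30- and 60-minute ratings stay open to knowledge of the arm whenever allocation is made. Later allocation protects only what comes before the snack.

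**Conclusion.** The point holds as a design and reporting weakness. Allocation before a common run-in, in a non-blind trial with no described concealment or delayed disclosure, creates a route to bias that could have been closed at almost no cost. It bears chiefly on run-in compliance and the self-rated baseline VAS, less on the assayed baseline hormones, and hardly on the visit-1 body composition.

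The size of any bias cannot be derived from the document. The measurable consequence, 2 of 52 allocated women untreated, is small, equal between arms and without practical effect on power.

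The conclusion assumes that the Pre-diet visit section gives the true order of events, which the Intervention and Overview sections support. If the sponsor can show that the list was held apart from callers, samplers and participants until the snack was served, the bias concern largely falls away and the accounting point remains.

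**What to change.** **In the design, for this plan or a repeat of it:**
1. At visit 2, take the baseline blood and the baseline VAS first.
2. Then open the next sequentially numbered, opaque, sealed envelope, prepared from the existing basket-drawn list, and serve that snack.
3. Analyse all women so allocated. No woman can then be lost between allocation and visit 2, although loss after the snack remains possible.

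**In the text:**
- Reconcile whether the 0-minute VAS precedes or follows the snack, and how arrival, baseline blood and snack fit when arrival and snack share one clock time.
- Reconcile the Overview's statement that all participants attended both visits with its report of two who did not attend the second.

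**For the completed trial, where allocation cannot be moved:**
- State who held the list and when staff and women learned the arm.
- Report 25 per arm as those treated out of 26 randomised.

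**Cost.** Envelopes, someone to prepare them, both snacks on hand at every second visit (peanuts were bought the day before serving, so some would go unused), and a short interval between arrival and snack. No extra visits are needed. Extra women are needed only if those who miss visit 2 are replaced to reach 26 per arm.
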